5.2 CTEP Agent

5.2.1 GDC-0449 (NSC 747691)

Chemical Name or Amino Acid Sequence: 2-chloro-N-[4-chloro-3-pyridin-2-yl-phenyl]-4-(methanesulfonyl)benzamide

Other Names: Systemic Hedgehog Pathway Antagonist, G-025897, G-025897.1, and GDC-0449.1, GDC-0449

Classification: Hedgehog Pathway Antagonist

CAS Registry Number: 879085-55-9

Molecular Formula: C₁₉H₁₄Cl₂N₂O₃S

M.W.: 421.3 g/mol

Mode of Action: GDC-0449 provides anticancer responses by inhibiting the hedgehog pathway. The Hedgehog signaling pathway controls cell differentiation, growth, and proliferation. It is most active during embryogenesis but may also play a role in the regulation of adult stem cells involved in the maintenance and regeneration of adult tissues.

How Supplied: GDC-0449 is supplied by Genentech and distributed by the CTEP, NCI. It is available as 150-mg grey and pink size 1 capsules containing microcrystalline cellulose, lactose monohydrate, sodium lauryl sulfate, povidone K29/32, talc, sodium starch glycolate, and magnesium stearate. The capsule shell consists of gelatin, red iron oxide, black iron oxide, and titanium dioxide. A compendial-grade black printing ink may be used.

Capsules are packaged in 75-mL round, white, high-density polyethylene (HDPE) bottles and closed with 38/400 two-piece HDPE child-resistant caps. Each bottle contains 32 capsules.

Storage: Store GDC-0449 at room temperature between 59°F and 86°F (15°C and 30°C).

Stability: Stability testing is ongoing.

Route(s) of Administration: Oral

5.2.2 Preparation and Administration

Drug Administration: Patients should take GDC-0449 at approximately the same time according to their dose level, with or without food. If a patient misses a dose (e.g., due to emesis), he or she should be instructed not to take or make up that dose and to resume dosing with the next scheduled dose. Missed doses should not be made up.

Patient Care Implications: The terminal half-life of GDC-0449 is currently unknown, but is expected to be longer than 1 week, and may be as high as 2 to 3 weeks. If plasma levels of GDC-0449 need to be lowered emergently, animal studies suggest that oral administration of activated charcoal may lower drug plasma levels more quickly than dose cessation alone.

Drug Interactions: Avoid any concurrent drug metabolized by cytochrome P450 that has a narrow therapeutic index.

5.2.3 Accountability and Compliance

GDC-0449 is an investigational agent supplied to investigators by the Division of Cancer Treatment and Diagnosis (DCTD), NCI.

GDC-0449 is provided to the NCI under a Collaborative Agreement between Genentech and the DCTD, NCI (see [Section 12.3](#)).

Agent Ordering and Agent Accountability

NCI-supplied agents may be requested by the Principal Investigator (or their authorized designee) at each participating institution. Pharmaceutical Management Branch (PMB) policy requires that agent be shipped directly to the institution where the patient is to be treated. PMB does not permit the transfer of agents between institutions (unless prior approval from PMB is obtained). The CTEP-assigned protocol number must be used for ordering all CTEP-supplied investigational agents. The responsible investigator at each participating institution must be registered with CTEP, DCTD through an annual submission of FDA Form 1572 (Statement of Investigator), Curriculum Vitae, Supplemental Investigator Data Form (IDF), and Financial Disclosure Form (FDF). If there are several participating investigators at one institution, CTEP-supplied investigational agents for the study should be ordered under the name of one lead investigator at that institution.

Active CTEP-registered investigators and investigator-designated shipping designees and ordering designees can submit agent requests through the PMB Online Agent Order Processing (OAOP) application (<https://eapps-ctep.nci.nih.gov/OAOP/pages/login.jsp>). Access to OAOP requires the establishment of a CTEP Identity and Access Management (IAM) account (<https://eapps-ctep.nci.nih.gov/iam/>) and the maintenance of an “active” account status and a “current” password. For questions about drug orders, transfers, returns, or accountability, call [contact] Monday through Friday between 8:30 am and 4:30 pm (ET) or email [contact] anytime.

Agent Inventory Records – The investigator, or a responsible party designated by the investigator, must maintain a careful record of the inventory and disposition of all agents received from DCTD using the NCI Oral Drug Accountability Form. (See the NCI Investigator’s Handbook for Procedures for Drug Accountability and Storage.)

5.3 Other Immunosuppression

5.3.1 Corticosteroids

Corticosteroids at a dose of >0.5 mg/kg/d PDE for at least 1 week prior to initiation of GDC-0449. After initiation of GDC-0449, the corticosteroids will be tapered according to protocol guidelines in the following table, in order to minimize heterogeneity and subsequent potential for confounding:

Week	PDE (mg/kg)
0 Start of therapy	1 daily until at least 1 week after clinical improvement
1 to 2 (starting at least 1 week after clinical improvement)	1 alternating with 0.5
3 to 4	1 alternating with 0.25
5 to 6	1 every other day (maintain until resolution of GVHD)
7 to 8 (start after resolution or near resolution of GVHD)	0.7 every other day
9 to 10	0.5 every other day
11 to 12	0.4 every other day
13 to 14	0.3 every other day
15 to 16	0.2 every other day
17 to 18	0.1 every other day

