4.1 Inclusion Criteria

Yes/No (Response of "no" = patient ineligible)

4.1.1 _____ Age ≥ 18 years.

Because no dosing or adverse event data are currently available on the use of GDC-0449 in patients < 18 years of age, children are excluded from this study.

4.1.2 _____ ECOG performance status ≤ 2 (Karnofsky $\geq 60\%$, see [Appendix A](#)).

4.1.3 _____ Life expectancy of greater than 12 months

4.1.4 _____ Patients must have normal organ and marrow function as defined below:

- | | |
|--|--|
|  Leukocytes | $\geq 3,000/\text{mcL}$ |
|  Absolute neutrophil count | $\geq 1,500/\text{mcL}$ |
|  Platelets | $\geq 50,000/\text{mcL}$ |
|  Total Bilirubin | within normal institutional limits |
|  AST(SGOT)/ALT(SGPT) | $\leq 2.5 \times$ institutional upper limit of normal |
|  Creatinine | $\leq 1.5 \text{ mg/dl}$ |
| OR | |
|  Creatinine Clearance | $\geq 55 \text{ mL/min}$ using the Cockcroft-Gault equation for patients with creatinine |

levels above 1.5 mg/dl.

- 4.1.5** _____ Patients with chronic GVHD diagnosed within 3 years after hematopoietic stem cell transplant (HSCT) for any disease, with any graft, and any conditioning regimen with at least one manifestation secondary to fibrosis, including: sclerodermatous skin changes, dry mouth, dry eye, esophageal strictures, or vaginal GVHD
- 4.1.6** _____ Failure to respond to corticosteroids, defined as:
- Progression of chronic GVHD despite optimal first line therapy (> 0.5 mg/kg/day of prednisone dose equivalent (PDE) for two weeks) or;
 - No improvement after 4-8 weeks of sustained therapy. Sustained therapy should include 2 weeks of > 0.5 mg/kg/day of PDE or;
 - Inability to taper steroid dosage to less than 0.5 mg/kg/day of PDE without worsening of chronic GVHD or;
 - Need for second or third line therapy beyond corticosteroids and calcineurin inhibitors or sirolimus, irrespective of other criteria listed under the current section.

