9.1.2 Definition of Response to Therapy

1. Stable disease (SD) (no change in chronic GVHD) according to NIH consensus response criteria for a total of 1month [46]. This criteria is irrespective of any response obtained initially, prior to the month of stability.
2. Progressive Disease: This is defined as any one of the following:
 - Skin: Increase in NIH Skin Score by 1 or more points, except 0 to 1.
 - Eyes: Increase in NIH Eye Score by 1 or more points, except 0 to 1.
 - Mouth: Increase in NIH Modified Oral Mucosa Rating Score of 2 or more points.
 - Esophagus: Increase in NIH Esophagus Score by 1 or more points, except 0 to 1.
 - Upper GI: Increase in NIH Upper GI Score by 1 or more points, except 0 to 1.
 - Lower GI: Increase in NIH Lower GI Score by 1 or more points, except from 0 to 1.
 - Liver: Increase by 2x ULN ALT, alkaline phosphatase, and Total bilirubin.
 - Lungs: Decrease by 10% predicted absolute value of %FEV1. If PFTs not available, increase in NIH Lung Symptom Score by 1 or more points, except 0 to 1.
 - Joints and Fascia: Increase in NIH Joint and Fascia Score by 1 or more points or decrease in P-ROM score by 1 point for any site.
 - Global: Clinician overall severity score increases by 2 or more points on a 0 – 10 scale
3. Partial Response: This is defined as any one of the following:
 - Skin: Decrease in NIH Skin Score by 1 or more points
 - Eyes: Decrease in NIH Eye Score by 1 or more points
 - Mouth: Decrease in NIH Modified Oral Mucosa Rating Score of 2 or more points.
 - Esophagus: Decrease in NIH Esophagus Score by 1 or more points.
 - Upper GI: Decrease in NIH Upper GI Score by 1 or more points
 - Lower GI: Decrease in NIH Lower GI Score by 1 or more points.
 - Liver: Decrease by 50% ALT, alkaline phosphatase, and Total bilirubin.
 - Lungs: Increase by 10% predicted absolute value of %FEV1. If PFTs not available, decrease in NIH Lung Symptom Score by 1 or more points.
 - Joints and Fascia: Decrease in NIH Joint and Fascia Score by 1 or more points or increase in P-ROM score by 1 point for any site.

- Global: Clinician overall severity score decreases by 2 or more points on a 0 – 10 scale.
4. Complete Response: This is defined as any one of the following:
- Skin: NIH Skin Score 0 after previous involvement.
 - Eyes: NIH Eye Score 0 after previous involvement.
 - Mouth: NIH Modified Oral Mucosa Rating Score 0 after previous involvement.
 - Esophagus: NIH Esophagus Score 0 after previous involvement.

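### Read literally, the steroid taper in section 5.3.1 raises the dose of patients entering between 0.5 and 1 mg/kg/d just as GDC-0449 starts

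*Combined protocol and SAP*

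**What the plan says.** Section 5.3.1 first sets a condition before the study drug: "Corticosteroids at a dose of >0.5 mg/kg/d PDE for at least 1 week prior to initiation of GDC-0449". It gives a floor and no ceiling. It continues: "After initiation of GDC-0449, the corticosteroids will be tapered according to protocol guidelines in the following table", and gives the reason: "in order to minimize heterogeneity and subsequent potential for confounding".

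The table's first row, Week 0, is labelled as the start of therapy and reads, in mg/kg, "1 daily until at least 1 week after clinical improvement". The next rows are 1 alternating with 0.5, 1 alternating with 0.25, and 1 every other day. The row after that is labelled "7 to 8 (start after resolution or near resolution of GVHD" and gives 0.7 every other day, with further steps down to 0.1 every other day. Section 8.4 converts study months into weeks so that the visit schedule can be read alongside the weekly steroid taper.

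Section 4.1 defines steroid failure by several routes. One is "Progression of chronic GVHD despite optimal first line therapy (> 0.5 mg/kg/day of prednisone dose equivalent (PDE) for two weeks) or". Another carries no steroid dose at all: "Need for second or third line therapy beyond corticosteroids and calcineurin inhibitors or sirolimus, irrespective of other criteria listed under the current section".

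The endpoints that steroid dose can touch are these:

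- FFS at 6 months (sections 9.1.1 and 10.1.1) requires a steroid dose of at most 0.2 mg/kg/d and no other systemic GVHD therapy added. A steroid increase at the start is not named as failure.
- Under section 9.1.2, a month of stable disease, or progression, calls for added systemic therapy and ends study participation. "Partial Response: This is defined as any one of the following" is followed by a list of single-organ or global improvements.
- Partial or complete response decides extension beyond 6 months (section 5.5), and 6-month response to GDC-0449 is a secondary endpoint (section 10.1.2).

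Section 10.2 plans no analysis that takes steroid dose into account.

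**The concern.** A patient can satisfy the pre-dose sentence at, say, 0.6 mg/kg/d. The text promises that this patient's steroids will come down after GDC-0449 starts, but the only dose the table gives for Week 0 is higher. The sentence, the taper wording and the row cannot all be followed for that patient, and no other section says how such a patient joins the table.

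The trial has no control arm and is open label. If steroids rise on the day the study drug starts, early improvement has two possible causes and the design cannot tell them apart. Improvement then has consequences: it avoids the added therapy that stable or progressive disease would trigger, it starts the taper, and a partial response needs only one qualifying item. The confounding that the table was written to limit could therefore enter through its first row.

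**Working it through.** There is no stated figure to reproduce. The check is arithmetic on the doses in section 5.3.1.

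**Size of the Week 0 step.** Relative change = 1 / entry dose − 1.

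| Entry dose (mg/kg/d) | Week 0 dose | Change |
|---|---|---|
| 0.51 | 1.0 | 1/0.51 − 1 = +96% |
| 0.6 | 1.0 | 1/0.6 − 1 = +67% |
| 0.75 | 1.0 | 1/0.75 − 1 = +33% |
| 1.0 | 1.0 | 0% |
| 1.2 | 1.0 | 1/1.2 − 1 = −17% |

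As the entry dose approaches 0.5 the increase approaches 100% without reaching it.

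**How long the dose stays above entry.** Averaging alternate-day doses over two days gives row means of 1.0; (1 + 0.5)/2 = 0.75; (1 + 0.25)/2 = 0.625; 1/2 = 0.5; then 0.35, 0.25, 0.20, 0.15, 0.10 and 0.05 mg/kg/d. An entrant at 0.51 to 0.62 is below 0.625, so stays above the entry dose through the first three rows: the hold at 1 mg/kg plus four taper weeks. The fourth row (0.5) is below every compliant entry dose.

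**Cumulative dose.** The length of the hold is not fixed, so 1, 2, 4 and 8 weeks are assumed. Dose through taper weeks 3 to 4 = 7 × hold × 1.0 + 14 × 0.75 + 14 × 0.625. The comparator is a flat 0.51 over the same days.

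| Hold (weeks) | Table (mg/kg) | Flat 0.51 (mg/kg) | Ratio |
|---|---|---|---|
| 1 | 26.25 | 17.85 | 1.47 |
| 2 | 33.25 | 21.42 | 1.55 |
| 4 | 47.25 | 28.56 | 1.65 |
| 8 | 75.25 | 42.84 | 1.76 |

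**Position at 6 months (week 24, section 8.4).** With two-week steps and none prolonged, the row averaging 0.20 begins 10 weeks after the taper starts. A mean of at most 0.2 at week 24 therefore needs the taper to begin by week 24 − 10 = 14. A patient can be stepped up at the start, improve, begin the taper by then and still count as an FFS success. The row averaging 0.5 begins 4 weeks into the taper, so a patient whose taper starts by week 24 − 4 = 20 is below any compliant entry dose when response is scored.

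**The case against.** The best defence is that no increase was intended. Tapering means going down. The row label does not say which therapy is starting and could mean steroid therapy, and a patient below 1 mg/kg/d might simply join at a later row. A pre-dose floor and a post-dose schedule also do not contradict each other for someone already at 1 mg/kg/d. All of this is fair, and it leaves the entry row open. It does not remove the problem. The table is introduced as applying once GDC-0449 has begun, section 8.4 ties the taper weeks to the study schedule, and 1 mg/kg is the only Week 0 dose given.

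A second defence is timing. Response is scored at 6 months, when a patient who began the taper by week 20 is on less steroid than at entry. FFS demands at most 0.2 mg/kg/d, at least 60% below any compliant entry dose (1 − 0.2/0.5 = 0.6). A non-improver cannot stay at 1 mg/kg indefinitely, because a month of stable disease calls for other therapy. This stands as a limit on the bias. It does not remove it, because improvement during the higher-dose period is what averts that added therapy and opens the taper.

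A third is that steroid-refractory patients should gain little from more steroid. Section 4.1 weakens this: no route requires failure at 1 mg/kg/d.

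It is also true that a common Week 0 dose serves the other half of the table's purpose, less heterogeneity between patients during treatment. Only the confounding half is at risk.

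**Conclusion.** For patients entering between 0.5 and 1 mg/kg/d, section 5.3.1 conflicts with itself. Read literally, the dose rises when GDC-0449 starts, by just under 100% at the lower edge and by 0% at 1.0. This assumes that the pre-dose sentence is a requirement and that Week 0 is the first day of GDC-0449.

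A reader might infer more: that steroids will in fact nearly double at the start, or that steroid benefit is being credited to GDC-0449. The documents support neither. They give no distribution of entry doses, so the number affected among the 12 is unknown and could be zero. The taper wording leaves room for a different entry row. The bias is an inference from the design, and its size cannot be calculated. It bears mainly on clinical response and the NIH score; for FFS, the 6-month steroid limit reduces it but does not remove it.

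The point still deserves action. Following the table as written would start a competing treatment change together with the study drug, in a trial with no control arm.

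**What to change.** Reconcile three pieces of section 5.3.1: the pre-dose sentence, the taper wording and the Week 0 row. State which therapy starts at Week 0 and how a patient below 1 mg/kg/d enters the table. Which dose applies is a clinical decision for the sponsor, and none is proposed here.

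Add one descriptive listing. For each patient, show the steroid dose just before GDC-0449, at its start and at 6 months, beside FFS and clinical response. Flag patients whose dose rose at the start, and say in the report that their response is not attributed to GDC-0449 alone. Separate FFS or response estimates by whether the dose rose are not worth adding: in 12 patients the groups would be very small and could not separate the two causes.

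The cost is a wording amendment and one listing. Section 5.4 requires the case report form to capture all concurrent drugs, and the section 7 calendar records them at baseline and every visit. No new data collection should be needed, provided dose and date are entered with each steroid record. The listing also covers patients treated before any amendment; section 9.3 shows that at least four have been.

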5.3.2 Calcineurin inhibitor and sirolimus

Therapy will continue at a dose which achieves the following trough serum levels:

- Tacrolimus: 5-10 ng/mL
- Cyclosporine: 120-200 ng/mL
- Sirolimus: 5-10 ng/mL

5.4 General Concomitant Medication and Supportive Care Guidelines

Because there is a potential for interaction of GDC-0449 with other concomitantly administered drugs through the cytochrome P450 system, the case report form must capture the concurrent use of all other drugs, over-the-counter medications, or alternative therapies. The Principal Investigator should be alerted if the patient is taking any agent known to affect or with the potential to affect selected CYP450 isoenzymes. [Appendix E](#) presents guidelines for identifying medications/substances that could potentially interact with the study agent(s).

5.4.1 Concomitant Medications

GDC-0449 inhibits CYP2C8, CYP2C9, and CYP2C19 drug metabolism enzymes in vitro at concentrations that may be clinically relevant. Caution should be exercised when dosing GDC-0449 concurrently with medications that are substrates of CYP2C8, CYP2C9, and CYP2C19 and have narrow therapeutic windows. The table below lists clinically significant substrates of CYP2C8, CYP2C9, and CYP2C19. The table below represents medications to be used with caution. Only medications or substances that are strong inducers/inhibitors or strong substrates of CYP3A4/5, CYP2C9, CYP2C8, or CYP2C19 are prohibited. See exclusion criteria 4.2.5 for additional information.

2C8	2C9	2C19
Miscellaneous	NSAIDs	Proton-pump inhibitors
Repaglinide	Diclofenac	Omeprazole
Rosiglitazone	Ibuprofen	Lansoprazole
	Piroxicam	Pantoprazole
	Naproxen	Rabeprazole

Celecoxib	Esoprazole
Oral hypoglycemic agents	Anti-epileptics
Glipizide	Diazepam
Tolbutamide	Phenytoin
Angiotensin II blockers	Phenobarbitone
Irbesartan	Miscellaneous
Iosartan	Amitriptyline
NOT candesartan	Clomipramine
NOT valsartan	Clopidogrel
Miscellaneous	Cyclophosphamide
Fluvastatin	
Phenytoin	
Sulfamethoxazole	
Tamoxifen	
Torseamide	
Warfarin	

NSAIDs = Non-steroidal anti-inflammatory drugs

Clinically significant PK interactions between vismodegib and CYP450 inhibitors are not expected. Results from Study GP28465 demonstrated no clinically significant PK interaction between vismodegib and fluconazole (a moderate CYP2C9 inhibitor) or itraconazole (a strong CYP3A4 inhibitor) in healthy volunteers. Inducers of CYP3A4 are not predicted to alter vismodegib systemic exposure since similar steady-state plasma vismodegib concentrations were observed in patients in clinical studies concomitantly treated with CYP3A4 inducers (i.e., carbamazepine, modafinil, phenobarbital) and those concomitantly treated with CYP3A4 inhibitors (i.e., erythromycin, fluconazole).

If plasma levels need to be lowered emergently, animal studies have suggested that oral administration of activated charcoal may lower drug plasma levels more quickly than drug cessation alone.

5.4.2 Pregnancy and Reproductive Concerns

Women of childbearing potential (defined in [Appendix B](#)) are required to have a negative serum pregnancy test (with a sensitivity of at least 25 mIU/mL) within 7 days prior to the first dose of GDC-0449 (serum or urine). A pregnancy test (serum or urine) will be administered every 4 weeks if their menstrual cycles are regular or every 2 weeks if their cycles are irregular while on study within the 24-hour period prior to the administration of GDC-0449. Prior to dispensing GDC-0449, the investigator must confirm and document the patient's use of two contraceptive methods, dates of negative pregnancy test, and confirm the patient's understanding of the of GDC-0449 to cause spontaneous abortion or birth defects.

Female patients are required to use two forms of acceptable contraception (refer to [Appendix B](#)), including one barrier method **during participation in the study and for the 24 months following the last dose**. All patients should receive contraceptive counseling either by the investigator, or by an obstetrician (OB)/gynecologist or other physician who is qualified in this area of expertise. If a woman of childbearing potential believes that her contraceptive method has failed, emergency contraception should be considered.

If a patient is suspected to be pregnant, GDC-0449 should be immediately discontinued. In addition, a positive urine test must be confirmed by a serum pregnancy test. If it is confirmed that the patient is not pregnant, the patient may resume dosing with GDC-0449.

If a female patient becomes pregnant during therapy or within 24 months after the last dose of GDC-0449, or if the female partner of a male patient exposed to the drug becomes pregnant while the male patient is receiving GDC-0449 or within 3 months after the last dose of GDC-0449, the investigator must be notified in order to facilitate outcome follow-up.

Abortion, whether accidental, therapeutic, or spontaneous, should always be classified as serious. Any congenital anomaly/birth defect in a child conceived during the study or within 24 months after the last dose of GDC-0449 to a female patient or to a female partner of a male patient exposed to the agent during treatment or within 3 months after the last dose of GDC-0449 should be recorded and reported as an SAE.

- Female patients should not breastfeed a baby while on this study.
- Female patients must NEVER donate ova while being treated with GDC-0449.
- All sexually active male subjects (including those who have undergone vasectomy) should utilize a barrier form of contraception **during study treatment and for 3 months after the last dose** as it is not known whether GDC-0449 that may be present in seminal fluid would cause serious or life-threatening birth defects in a fetus born to the female partner of a male subject. Males should also not donate sperm during treatment or up to 3 months after the last dose.
- All patients are prohibited from donating blood for 24 months after the last dose of GDC-0449.

